13.0 DATA MANAGEMENT

13.1 Registration

13.1.1 When a patient is found to be eligible for study, a signed informed consent will be required by the managing physician.

13.1.2 Questions concerning eligibility may be addressed to the Study Chair(s), Contact Person/Data Manager or Nurse Contact. A protocol number will be assigned.

13.1.3 All patient entries will be registered in CORE. The following forms will be completed in a timely fashion and will be placed in the subject's study chart. (Appendices D-G and I-T).

14.0 TRANSLATIONAL RESEARCH (See Appendices H and I)

14.1 Specimen Collection

Blood Draws:

An approximately 28 mL (5-6 tsp) blood sample (2 green tops, 1 CPT tube) will be obtained at time of enrollment prior to the initiation of propranolol. All blood will be immediately processed and frozen in at least 5 aliquots at -80° C. The plasma will be used to perform ELISA assays for VEGF, IL-6, IL-8., and circulating HPV.

14.2 Specimen handling:

Plasma for detecting of cytokines and angiogenic markers: 20 ml (4-5 tsp) of whole venous blood is collected in two **greentop tubes**. The tubes of whole blood should be allowed to sit for 10 minutes or until clotting is complete. Centrifuge the tube at 3000 rpm for 10 minutes. Transfer the plasma using a transfer pipet. Store the plasma in polypropylene cryostorage tubes. Aliquot .2 ml per tube. Freeze within 2 hrs of phlebotomy.

14.3 Types of Laboratory assays:

Multiplex ELISA for detecting IL-6, IL-8, VEGF. Multiplex ELISA will be carried out based on the manufacturer's instruction for detecting both human and mouse IL-6, IL-8, VEGF, in plasma collected at the visit prior to starting therapy, at the 2nd mos of treatment and the 4th month of treatment Coupled with the Luminex xMAP®platform in a magnetic bead format, the MILLIPLEX® MAG Human Cytokine / Chemokine panel (Millipore Corporation, Billerica, MA) allows us to quantitative multiplex detection of dozens of analytes simultaneously, which can dramatically improve productivity.

Microarray will be performed at Genomics Core Facility. RNA will be isolated from PBMCs using MirVana RNA extraction. RNA extracted from patients before and after treatment will be sent to Core Facility for microarray analysis.

14.4 Shipping:

Contact [name] for sample processing. All blood samples will be batched shipped to [name] laboratory at M.D. Anderson Cancer Center in Houston, Texas. All samples will be de-identified by a number that is only recognizable by the Principal Investigator.

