1.3 Exploratory objectives

- 1.3.1 To measure changes in serum levels of IL-6, IL-8, IL-10 and VEGF, CRP during treatment with propranolol in addition to receiving PMR intervention
- 1.3.2 To measure changes in resting energy use during treatment with propranolol in addition to receiving PMR intervention
- 1.3.3 To measure HPV components (e.g.E6 or E7 are reduced following treatment with beta blocker) in circulating cell-free DNA during intervention as a quantative assessment using qRT-PCR.

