IL-6 levels in plasma will be measured using enzyme-linked immunosorbent assays (ELISAs; R&D Systems, Minneapolis, MN), with results interpolated from using the standard curve provided with the ELISA kit. IL-6-expressing specimens with sensitivity below that of below the sensitivity cutoff for the regular assay will be quantitated using high-sensitivity ELISA (R&D Systems).

5.4.4.2 IL-10:

IL-10 is a counterregulatory or immunosuppressive mediator of stress-induced immunosuppression. IL-10 is extremely important to the initial transformation of cervical dysplasia to premalignant lesions. Investigators have shown that IL-10 expression is directly proportional to the development of HPV-induced cervical cancer [48]. Furthermore, in mouse models, stress-induced increases in IL-10 expression can be prevented by treatment with nadolol as well as a benzodiazepine [118]. Furthermore in a study of behavioral (telephone mediated) interventions, improvement in QOL seen in the intervention cohort was correlated with an inverse association between modulation of QOL and serum levels of IL-10 as indicated by the mean and standard error of the mean for a cohort of individual measurements [50].

5.4.4.2.1 Methods:

Serum levels of IL-10 (lower limit of detection, 0.5 pg/mL) will be measured in triplicate using standard ELISA (R&D Systems).

5.4.4.3 IL-8:

Chronic stress is associated with increase IL-8 levels [119]. IL-8 has a key role in regulation of angiogenesis, chemotaxis, and

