enhancement of growth in a variety of tumors [120-122]. It is produced by tumor cells and macrophages [123]. In melanoma and ovarian cancer cell lines, treatment with norepinephrine has resulted in increased expression of VEGF, IL-8, and IL-6 [83, 119]. IL-8 contributes to the migration of tumor cells toward blood vessels and provides proliferative and antiapoptotic signals to tumor cells [124]. IL-8 overexpression is associated with advanced disease stage, high tumor grade, and decreased OS durations in cervical cancer patients [122]. IL-8 is thought to have an effect on tumor growth owing to expression of an angiogenic factor supplied by macrophages within and around cervical tumors. IL-8 expression has correlated with microvessel counts in cervical cancer patients [122], and microvessel density correlates with radioresistance and decreased OS duration [125]. Poorly oxygenated cervical tumors have increased microvessel densities, and this has correlated with decreased survival duration. Therefore, we hypothesize that IL-8 is a surrogate for angiogenesis changes that should be inhibited by the administration of propranolol.

5.4.4.3.1 Methods:

IL-8 expression in plasma will be measured using ELISA (R&D Systems), with the results interpolated from using the standard curve provided with the ELISA kit.

5.4.4.4 VEGF:

VEGF is one of the most potent proangiogenic molecules, inducing endothelial cells in vascular microvessels near tumors to proliferate and migrate and inducing alteration of their patterns of gene expression in favor of angiogenesis [126]. VEGF makes cells hyper-permeable, resulting in conditions favorable for angiogenesis in the extracellular matrix [127]. VEGF is produced by tumor cells, macrophages, and other cells. VEGF expression has been linked with norepinephrine stimulation of proliferation of cancer cell lines [83]. VEGF is critical to the growth and progression of cervical cancers and is a poor prognostic marker as consistent increases in VEGF expression are seen with increasing disease severity, and increased serum VEGF expression levels in other tumors are associated with metastatic disease and poor survival [98, 128, 129].

5.4.4.4.1 Methods:

Plasma VEGF expression will be measured using a standard ELISA kit (R&D Systems) (88). The minimum detectable serum level of VEGF = 5 pg/mL.

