3. $\Pr(\pi_t \leq 0.2 \mid \text{data}) > 90\%$ where π_t is the proportion of any grade 3-4 toxicities that are probably, possibly, or definitely related to the intervention.

Scores for the FACT-Cx can be calculated when at least 50% of the items on each subscale have been answered. A total score for the FACT-Cx can be calculated when at least 80% of the total items have been answered and each subscale has a score.

Scores for BPI: Pain Severity can only be calculated when all 4 items have been answered. Scores for BPI: Pain Interference can be calculated when at least 4 out of the 7 items have been completed.

Scores for HADS: Anxiety can be calculated when at least 6 of the 7 anxiety items have been completed. Likewise, scores for HADS: Depression can be calculated when at least 6 of the 7 depression items have been answered.

Scores for MDASI: Symptom Severity can be calculated when at least 7 of the 13 items have been completed. Scores for MDASI: Symptom Interference can be calculated when at least 4 of the 6 items have been completed.

Patients are considered nonevaluable if they leave the study through disease-specific death or progressive disease prior to Month 4, and they will not be replaced. Disease-specific death does not include death due to excessive toxicity. All other patients are considered evaluable. In addition to calculating the percent of women who complete these quality of

life (QoL) measures, we will calculate the percent of women completing combined intervention of twice daily beta blocker and twice weekly progressive muscle relaxation and guided imagery at Month 2 and Month 4.

The secondary objectives of this study are to estimate the impact of beta blocker and relaxation intervention on symptoms, anxiety, depression, pain and QoL. We will examine symptoms and symptom distress using the MDASI, anxiety and depression using HADS, pain using the BPI and QoL using the Trial Outcome Index (TOI) of the FACT-Cx.

The exploratory objectives of this study are to measure changes in serum levels of IL-6, IL-8, IL-10, VEGF, CRP, and resting energy use via calorimeter, as well as to measure HPV components (e.g. E6 and E7) in circulating cell-free DNA.

All secondary and exploratory endpoints will be examined graphically and through summary statistics. Ninety percent confidence intervals will be calculated for all endpoints, including feasibility endpoints.

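### Section 14.2 has staff wait for clotting before drawing off plasma, and the protocol names both serum and plasma for the same exploratory markers

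*Combined protocol and SAP*

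**What the plan says.** Section 14.2 introduces the two green-top tubes as "Plasma for detecting of cytokines and angiogenic markers". It then instructs: "The tubes of whole blood should be allowed to sit for 10 minutes or until clotting is complete". A 10-minute spin follows, plasma is drawn off with a pipette, and freezing is due within 2 hours of the draw. Section 14.1 says instead that all blood is processed and frozen immediately. It lists two green tops and one CPT tube, with no tube named for serum, and assigns the plasma to VEGF, IL-6, IL-8 and circulating HPV.

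The sample type is named differently elsewhere:

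- Objective 1.3.1 reads "To measure changes in serum levels of IL-6, IL-8, IL-10 and VEGF, CRP during treatment with propranolol", and Section 12.0 repeats "to measure changes in serum levels of IL-6, IL-8, IL-10, VEGF, CRP".
- The hypothesis in Section 2.11 refers to serum for IL-6, IL-8 and VEGF.
- Section 5.4.4.1.1 says "IL-6 levels in plasma will be measured using enzyme-linked immunosorbent assays", and Section 5.4.4.3.1 says "IL-8 expression in plasma will be measured using ELISA".
- The VEGF method (5.4.4.4.1) is for plasma, but the detection limit given with it, 5 pg/mL, is stated for serum.
- The IL-10 method (5.4.4.2.1) begins "Serum levels of IL-10 (lower limit of detection, 0.5 pg/mL".
- The HPV method (5.4.4.5.1) and Section 14.3 say plasma. Section 14.3 covers IL-6, IL-8 and VEGF at baseline, month 2 and month 4.

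**The concern.** By definition, plasma is the fluid of unclotted blood and serum is the fluid left after clotting. A technician who waits for complete clotting and then removes the fluid has not collected plasma. One who spins at 10 minutes may have done so. Both have followed Section 14.2.

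The exploratory marker results are changes within a patient between visits, in a single-arm study planned for 15 evaluable women. If standing time or the degree of clotting differs between one patient's samples, any effect on the assay goes into her change score. Random differences would widen the interval. A drift in practice between baseline and later visits would shift the mean change, and there is no control arm against which to see it. Section 2.6 says the combination will be evaluated on translational endpoints before a planned randomized phase II, so these values are meant to be used again.

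**Working it through.** The protocol gives no figure for handling variation, so the main check compares the instructions. The arithmetic is limited to the standing-time window and one illustration.

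**1. Steps within Section 14.2.** Collect for plasma; stand for 10 minutes or to complete clotting; spin; transfer plasma. If the second alternative is taken, the fourth step cannot be done as named.

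**2. Standing time.** The minimum is 10 minutes, as stated. The maximum follows from the freezing limit less the spin: 120 − 10 = 110 minutes, reduced further by the time to transfer and aliquot. The permitted range is therefore 10 to just under 110 minutes. Section 14.1's immediate processing sits at the lower end at best.

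**3. Sample type by marker.**

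- IL-6 and IL-8: serum in 1.3.1, 2.11 and 12.0; plasma in their own methods and in 14.1 and 14.3.
- VEGF: serum in 1.3.1, 2.11, 12.0 and the detection limit; plasma in its method and in 14.1 and 14.3.
- IL-10: serum in 1.3.1, 12.0 and its method. Section 5.3 includes it in the baseline draw, but 14.1 and 14.3 do not list it and no serum tube is named. As written, the assay has no designated specimen.
- HPV DNA: plasma wherever a sample type is given.
- CRP: serum in 1.3.1 and 12.0, but scheduled in Section 8.1 among the laboratory tests, separately from the translational blood draw.

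**4. How many values.** The maximum for the four markers IL-6, IL-8, IL-10 and VEGF is 4 × 3 visits × 20 recruits = 240. If blood collection followed the survey targets of 15, 13 and 11 (an assumption), the count would be 4 × 39 = 156, or 3 × 39 = 117 without IL-10.

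**5. Illustration of noise.** Section 12.0 states a 90% half-width of 0.43 SD for a mean with 15 subjects. The normal formula gives 1.645/√15 = 0.425, close to the stated value; the t version (14 df) gives 0.455. Suppose handling adds independent noise to the change score with SD equal to r times the SD without it. In units of that original SD, the half-width becomes 0.425 × √(1 + r²):

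- r = 0.25: 0.438
- r = 0.5: 0.475
- r = 1.0: 0.601

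The values of r are assumptions; the documents supply none. A systematic shift between visits would instead move the mean by the size of the shift, with no sign of it in the interval.

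**The case against.** The strongest reply is that the operative text is more uniform than the wording suggests. One tube set is described, one instruction applies to everyone, and Section 14.3 names plasma at all three visits for IL-6, IL-8 and VEGF. A reader might infer that serum will be analysed at some visits or sites and plasma at others. The documents do not support that: no section plans different handling by visit or site. What remains is narrower. The single instruction permits different practice, and the IL-10 wording has no specimen to match it.

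A reader might also infer an unlimited wait. The 2-hour freezing rule caps it. Nor are all exploratory results exposed: resting energy use comes from calorimetry, and CRP is scheduled as a separate laboratory test. The count of 240 values is a ceiling.

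Two further points stand. Nothing in the documents says how much standing time or clotting alters these assays, so the contradiction is established from the text but its effect is not. And Section 14.0 refers to Appendix H, the specimen-submission procedure, whose text was not available for this review. It may set tighter times, so it cannot be said that the full plan lacks them. It would not remove the conflicts in the body of the protocol.

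**Conclusion.** The point holds as an internal contradiction in a working instruction, together with an inconsistent sample type for IL-6, IL-8, IL-10 and VEGF. Followed literally, Section 14.2 does not define one kind of sample, and it allows standing times from 10 to just under 110 minutes. The consequence is possible extra noise or bias, of unknown size, in exploratory within-patient changes.

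The conclusion rests on the ordinary definitions of plasma and serum and on the body text alone, without Appendix H. It does not reach the feasibility criteria in Section 12.0 or the sample size, neither of which uses these markers. The priority is low, but correction is cheap and should come before samples are frozen, because handling differences cannot be separated out afterwards unless times were recorded.

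**What to change.** - In Section 14.2, delete the alternative of waiting for clotting. Set one fixed draw-to-centrifugation time for all visits and sites, and reconcile it with Section 14.1 and Appendix H.
- Record the draw time and the spin time for every sample.
- Name plasma as the sample type for IL-6, IL-8, IL-10 and VEGF wherever serum now appears for the study's own measurements: 1.3.1, 2.11, 5.4.4.2.1, the detection limit in 5.4.4.4.1, and 12.0. Confirm that the IL-10 and VEGF detection limits (0.5 and 5 pg/mL) apply to plasma.
- Add IL-10 to the assay lists in Sections 14.1 and 14.3.
- Separate CRP from the other markers in 1.3.1 and 12.0 and leave it under its own laboratory method, so that it is not relabelled as plasma by accident.

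The cost is a set of wording changes and two recorded times per sample. No additional blood or patients are needed.

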15.0 PROTOCOL COMPLIANCE

The attending physician and oncology nurse must see each patient prior to each study time point indicated. All required interim and pre-treatment data should be available to the physician. The physician must make a toxicity grade. All study parameters required by protocol before each cycle of therapy must be documented.

